**Planned and Actual Randomized Treatment**

For participants who received the correct treatment throughout the study, the actual treatment will be the same as the planned treatment. For participants who received an incorrect treatment, the actual treatment will be derived as follows:

- If the number of doses on an incorrect treatment is less than the number of doses on the planned treatment, then the actual treatment is assigned as planned treatment.
- If the number of doses on an incorrect treatment is greater than the number of doses on the planned treatment, then the actual treatment is assigned as the incorrect treatment.
- If the number of doses on an incorrect treatment and planned treatment are the same, the actual treatment is assigned as the treatment with the highest UMEC and/or FF dose.
- If an incorrect container was dispensed and not returned, such that it is not possible to ascertain whether or not any doses were taken from the incorrect container, it will be assumed that the participant took all possible doses from this container (i.e., 30 doses in total).

**Participants excluded from ITT population**

- A participant who is recorded as a screen failure, run-in failure, or stabilization failure, but is randomized and does not receive a dose of study treatment, is considered to be randomized in error and will be excluded from the ITT population
- These participants will be identified using the deviations dataset where the term "Randomized in Error:" is reported.

### 11.6.2. Study Population

Demographics
Age

 
• Age will be calculated based on the Pre-Screening Visit date (or Screening, if pre-screening not performed).
 
• Only year of birth is collected on eCRF. Day and Month of birth are imputed as 30 June. Age is derived using the date of the pre-screening visit.
 
• All participants with imputed age of 17 or 18 years will be source data verified, and presence / absence of protocol deviation on the inclusion criteria #1 will be taken into consideration in the derivation for the analysis variable age.
 
• Birth date will be presented in listings as 'YYYY'.
 

Age at onset

 
• This will be derived as age at pre-screening visit (or screening, if pre-screening not performed)-disease duration.
 
• If a participant has age of onset of <0 this will be queried by data management.
 
• As we do not collect date of birth to the exact date negative values could occur. In these cases, the age of onset will be set to 0.
 

Body Mass Index (BMI)

 
• Calculated as weight (kg) / [height (m)]
 
• BMI will be presented as for summary statistics with 1 decimal place.
 

Clinic Spirometry Assessment

 
• At Visit 1, if the spirometry assessment is repeated for a given participant to meet the eligibility criteria on the reversibility, the repeated spirometry data will be used for that visit.
 

Cardiovascular History and Risk Factor

Cardiovascular history and risk factors will be assessed at Visit 1. Participants with one or more of the following terms recorded as either current or past medical conditions at Visit 1 is considered to have cardiovascular history/risk factors:
 
 
• Cardiovascular history 
 
○ arrhythmia,
 
○ congestive heart failure,
 
○ coronary artery disease,
 
○ myocardial infarction,
 
○ cerebrovascular accidents,
 
 
 
• Cardiovascular risk factors 
 
○ hypertension,
 
○ diabetes mellitus,
 
○ hypercholesterolemia.
 
 
 

Treatment Compliance

 
• If a dose counter start count is missing, then it will be assumed to be 30 for the ELLIPTA DPI. If any dose counter stop is missing, then the number of doses taken will be set to missing for that inhaler.
 
• Number of doses of study drug taken by each participant from each inhaler = Dose
 

Demographics

counter start value – dose counter stop value.
 
 
The derivation for treatment compliance during the double-blind treatment period is defined as the sum of (dose counter start value – dose counter stop value) over all inhalers dispensed to the participant and returned during the double-blind treatment period (i.e. from randomization to EOS/EW visit) and percentage compliance will be calculated as follows:
 
 $\text{Treatment compliance} = \frac{\text{Total number of doses received}}{\text{Treatment stop date} - \text{treatment start date} + 1} \times 100$ 
If a participant is lost to follow up (without EOS/EW visit) then their treatment stop date will be handled in accordance to Section 11.7.2 and doses received will be calculated for inhalers dispensed and returned from randomization to treatment stop date.
 
 
The derivation of the treatment compliance during the first 24 weeks is as follows:                     
 
For participants who withdraw from IP prior to week 24 or with End of Study visit at Week 24 is the same as the treatment compliance during the double-blind treatment period.
 
For participants who continue the double-blind study treatment beyond Week 24 is defined as the sum of (dose counter start value – dose counter stop value) over all inhalers dispensed to the participant prior to Visit 6 (Week 24) and returned by the participant on or before Visit 6 (Week 24) during the double-blind treatment period divided by the treatment duration covered by these inhalers, i.e., Week 24 clinic visit date – treatment start date Note: participants received first dose of the newly dispensed inhaler in clinic per protocol.
 
 
 
Overall compliance will be categorized as follows:                     
 
< 50 %
 
≥50 % to < 80%
 
≥80 % to < 95 %
 
≥95 % to ≤105 %
 
>105 % to ≤120 %
 
>120 %.
 
 
 
If a participant receives a treatment other than the randomized treatment during the study, the compliance will still be calculated using data from all containers received and overall exposure start and stop dates.
 

Severe exacerbation in the previous year


The number of severe exacerbations in the previous year is defined as:
 
Number of exacerbations in the last 12 months that required oral/systemic corticosteroids (not involving hospitalisation) + Number of exacerbations in the last 12 months that required hospitalisation

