6. STUDY TREATMENT

6.1. Investigational Product and Other Study Treatment

The term ‘study treatment’ is used throughout the protocol to describe any combination of products received by the subject as per the protocol design. Study treatment may therefore refer to the individual study treatments or the combination of those study treatments.

The DISKUS device will be used during the 3-week run-in period of the study. The DISKUS is a plastic inhalation delivery system containing a single-foil blister strip of a powder formulation of FSC intended for oral inhalation only. Each blister on the single-foil strip within the device contains 250 mcg of microfine FP and 72.5 mcg of microfine salmeterol xinafoate salt, equivalent to 50 mcg of salmeterol base, in 12.5 mg of formulation containing lactose (see [Table 2](#)). Each blister contains 1 complete dose of both medications. FSC will be sourced from local commercial stock. If not available locally, GSK will source centrally. The contents of the label will be in accordance with all applicable regulatory requirements.

Table 2 Description of FSC Inhalation Powder in DISKUS

Formulation	Single strip
	FP and salmeterol blended with lactose
Dosage Form	DPI with 60 doses (1 strip with 60 blisters)
Unit Dose Strengths	250 mcg FP and 50 mcg salmeterol per blister
Physical description	Dry white powder
Route of Administration	Inhaled

The ELLIPTA device will be used during the stabilization period and the treatment period. The ELLIPTA DPI is a moulded plastic two-sided device that can hold two individual blister strips. Descriptions of the study treatments administered via the ELLIPTA are provided in [Table 3](#).

Table 3 Description of Study Treatment Inhalation Powder in ELLIPTA

FF/UMEC/VI	First strip	Second strip
	FF blended with lactose	UMEC and VI blended with lactose and magnesium stearate
Dosage Form	ELLIPTA with 30 doses (2 strips with 30 blisters per strip)	
Unit Dose Strengths	100 or 200 mcg per blister	UMEC 31.25 or 62.5 mcg per blister, VI 25 mcg per blister
Physical description	Dry white powder	Dry white powder
Route of Administration	Inhaled	
FF/VI	First strip	Second strip
	FF blended with lactose	VI blended with lactose and magnesium stearate
Dosage Form	ELLIPTA with 30 doses (2 strips with 30 blisters per strip)	
Unit Dose Strengths	100 or 200 mcg per blister	25 mcg per blister
Physical description	Dry white powder	Dry white powder
Route of Administration	Inhaled	

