6.6. Compliance with Study Treatment Administration

When subjects are dosed at the study site, they will receive study treatment under medical supervision. The date and time of each dose administered in the clinic will be recorded in the eCRF. The dose of study treatment and study subject identification will be confirmed at the time of dosing by a member of the study site staff.

At scheduled clinic visits, subject compliance with study treatment administration since the previous scheduled clinic visit will be assessed by recording the number of doses remaining in the DISKUS or ELLIPTA, as applicable, in the eCRF (see the SRM for details), by reviewing the eDiary (see Section 7.3.5) and by querying the subject, as necessary. Subjects should be $\geq 80\%$ to $\leq 120\%$ compliant on taking study treatment between each pair of scheduled and consecutive on-treatment clinic visits. Subjects who fall outside this range should be re-educated on treatment compliance by their site. This re-education should be documented in the subject's source document.

When subjects self-administer study treatment(s) at home (i.e. not at the study site), compliance with study treatment administration should be monitored by the Investigator (or designee) by reviewing the transmitted eDiary data via the vendor-provided portal (see Section 7.3.5); subjects should be immediately contacted for re-education on treatment compliance if non-compliance (as assessed by the Investigator or designee) is observed. This re-education should be documented in the subject's source document.

A record of the number of DISKUSs and ELLIPTAs dispensed to each subject must be maintained and reconciled with study treatment and compliance records. Study treatment start and stop dates will be recorded in the eCRF.

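### SAP 11.6.2 counts doses only from returned inhalers but divides by all treatment days, so a participant with an unreturned inhaler is reported as less compliant than they were

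*SAP*

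**What the plan says.** SAP 11.6.2 (Treatment Compliance) takes the doses used from an inhaler as its counter start value minus its counter stop value. Two rules cover missing counters. For the start: "If a dose counter start count is missing, then it will be assumed to be 30 for the ELLIPTA DPI". For the stop: "If any dose counter stop is missing, then the number of doses taken will be set to missing for that inhaler".

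**Whole treatment period.** The counter differences are summed "over all inhalers dispensed to the participant and returned during the double-blind treatment period". The divisor is treatment stop date minus treatment start date plus one, that is, every calendar day on treatment. For participants lost to follow-up, "doses received will be calculated for inhalers dispensed and returned from randomization to treatment stop date".

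**First 24 weeks.** Participants who stop study treatment before Week 24, or whose study ends there, use the whole-period formula. For those who continue, the sum over inhalers returned by the Week 24 visit is "divided by the treatment duration covered by these inhalers, i.e., Week 24 clinic visit date" minus the treatment start date.

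Results are grouped as below 50%, 50 to below 80%, 80 to below 95%, 95 to 105%, above 105 to 120%, and above 120%. Protocol 6.6 separately asks for 80% to 120% compliance between consecutive on-treatment visits and prescribes re-education outside that range.

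**The concern.** The numerator is restricted to returned inhalers and the denominator is not. An unreturned inhaler therefore lowers compliance as if none of its doses had been taken. I found no rule in SAP 11.6.2 or 11.7 that shortens the denominator or sets the participant's compliance to missing.

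The first-24-weeks wording names a matched denominator, the duration covered by the counted inhalers. It then equates this with the full span to the Week 24 visit, and the two differ whenever an inhaler is excluded.

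Elsewhere the SAP treats an unreturned container in the opposite way. Section 11.6.1 assumes that all 30 doses were taken from an incorrect container that was not returned. That rule only assigns actual treatment, so it does not govern compliance, but it shows that no common convention exists.

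At stake is whether a reader of the compliance tables can tell missed doses from missing inhalers.

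**Working it through.** The documents state no compliance figure, so there is none to reproduce. I applied the SAP formula directly.

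**Inputs**
- Doses per inhaler: 30 (Protocol 6.1, Table 3: "ELLIPTA with 30 doses (2 strips with 30 blisters per strip").
- Treatment days D: 169, 253 and 365 for 24, 36 and 52 weeks (SAP 11.6.4, exposure categories).
- Assumed: one dose taken on every day, and m fully used inhalers left out of the numerator.

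**Formula:** compliance = 100 × (D − 30m) / D

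| D | m = 1 | m = 2 | m = 3 |
|---|---|---|---|
| 169 | 139/169 = 82.2% | 109/169 = 64.5% | 79/169 = 46.7% |
| 253 | 223/253 = 88.1% | 193/253 = 76.3% | 163/253 = 64.4% |
| 365 | 335/365 = 91.8% | 305/365 = 83.6% | 275/365 = 75.3% |

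The true value in every cell is 100%.

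**First 24 weeks, participants who continue.** The span to the Week 24 visit is 169 − 1 = 168 days. The results are 138/168 = 82.1%, 108/168 = 64.3% and 78/168 = 46.4%.

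**Where the category boundaries fall**
- Below 95% when 30m/D > 0.05, so D < 600m. One excluded inhaler is enough at any duration in this trial.
- Below 80% when 30m/D > 0.20, so D < 150m: under 150 days for one inhaler, 300 for two, 450 for three. For example, one inhaler excluded over 85 days gives 55/85 = 64.7%.

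**A whole visit interval unreturned.** For Weeks 12 to 24 (84 doses), the results are 85/169 = 50.3%, 169/253 = 66.8% and 281/365 = 77.0%. For Weeks 36 to 52 (112 doses), the result is 253/365 = 69.3%.

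**Sensitivity.** If only 28 of the 30 doses in the excluded inhaler had been used, the 169-day figure is 141/169 = 83.4%.

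**With a matched denominator.** Removing the same days from both parts gives (D − 30m)/(D − 30m) = 100% for every combination shown.

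**The case against.** **Missing stop counts.** A reader might infer that an inhaler without a stop count is scored as 30 missed doses. The SAP does not say so. It sets that inhaler's doses to missing, and a total with a missing component can itself be missing. SAP 11.7.2 supports this by ruling out imputation of missing numerical data outside the sensitivity analyses. The objection stands: the bias is written only for unreturned inhalers. For missing stop counts the fault is an unspecified rule, which two programmers could implement differently.

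**Non-compliance.** A reader might also infer that fully adherent participants will be reported as non-compliant. The SAP categories carry no such label. One excluded inhaler at 24, 36 or 52 weeks gives 82% to 92%, inside the Protocol 6.6 range, which in any case applies between visits and serves here only as a benchmark.

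**Effect on efficacy.** Nor do the documents support an effect on the efficacy results. On-treatment status depends on the treatment stop date (SAP 11.4), no per-protocol analysis is planned (SAP 11.1), and compliance is not a covariate or subgroup.

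**Lost to follow-up.** If the overall stop date is missing, SAP 11.7.2.1 may substitute the last recorded exposure stop date. If that date matches the last returned inhaler, the mismatch shrinks. The documents do not settle this.

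**Frequency.** The Protocol schedules inhaler collection at every post-randomization visit and requires reconciliation with compliance records, so losses may be few. No rate is given. None of this removes the mismatch in the written whole-period formula.

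**Conclusion.** The point holds for unreturned inhalers: followed as written, the whole-period formula biases compliance downward. One fully used inhaler excluded costs a perfect user 17.8 percentage points at 169 days (100 − 82.2), 11.9 at 253 and 8.2 at 365. That is a lower category, but falling below 80% requires two inhalers at 24 or 36 weeks, three at 52 weeks, or one with under 150 days of treatment.

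The missing-stop-count rule is incomplete, and the first-24-weeks denominator contradicts itself.

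These sizes assume one dose per day and 30 doses used per excluded inhaler. The effect on arm-level summaries cannot be computed without the rate of non-return. The consequence is confined to descriptive Tables 1.51–1.54 and Listing 14.

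**What to change.** Amend SAP 11.6.2 to use one of two rules:

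1. Compute compliance only over visit intervals in which every dispensed inhaler was returned with a usable stop count, and take the days in those intervals as the denominator.
2. Set participant-level compliance to missing when any inhaler is unaccounted for.

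Apply the same rule to the first-24-weeks derivation and delete the conflicting equation there. State how a missing stop count carries into the participant's total. Report by arm the number of participants and inhalers affected.

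Rule 1 must drop the whole interval from both parts, because several 30-dose inhalers can cover one interval: Weeks 12 to 24 span 84 days, which needs three. Suppose one of the three is unreturned, and the interval's days are dropped while the doses from the other two are kept. A perfect user treated for 169 days would then score 139/(169 − 84) = 139/85 = 163.5%.

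The cost is a short wording change, one derivation and a footnote. Compliance will rest on fewer days or fewer participants. It could be biased upward if those who do not return inhalers are less adherent, which is why the counts should be shown.

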**11.6.3. Efficacy**

Spirometry
Trough FEV1 and FVC

 
The trough value for FEV1 at Weeks 4, 12, 24, 36 and 52 visits is the value of the pre-dose (prior to taking the morning dose of study treatment) assessment.
 

Post study treatment FEV1

 
The post study treatment value for FEV1 at Week 24 and at the End of Study visit is the assessment value approximately 3 hours after administering the study medication.
 

Trough FEV1 over time

To evaluate the effect of UMEC over the first 24 weeks of the treatment period, the (weighted) mean trough FEV1 over the first 24 weeks of the treatment period will be calculated as the FEV1 area under the curve (AUC0-24w) normalized for time. Specifically, FEV1 weighted mean AUC0-24w will be calculated based on all non-missing data as area under the curve from day 1 to week 24 using the linear trapezoidal rule divided by the observation time (24 weeks) to report in liter (L) units. If one or more observations are missing between two non-missing observations, the value(s) will be linearly interpolated between the two non-missing values.
 
The weighted mean AUC0-24w will be calculated over the nominal assessment time per protocol as follows:
 $WM\ FEV_1\ AUC_{0-24w} = \frac{\frac{1}{2} \sum_{i=0}^3 (FEV_1(t_i) + FEV_1(t_{i+1})) * (t_{i+1} - t_i)}{24w}$ 
Where, t0 = 0 (week), t1= 4 (week), t2=12 (week), and t3=24 (week); FEV1 (t0) = baseline trough FEV1, and for i>0, FEV1 (ti) = trough FEV1 reading at planned week ti.
 
If baseline, week 24 or any two timepoints are missing the AUC will not be calculated.

Asthma Exacerbations		
General		

 
Exacerbations will be presented based on onset date relative to the period being summarized. i.e. if the onset date occurs within the study period then it will be reported within that study period)
 
 
The following data will be included in the exacerbation analyses and summaries
		
Analysis	Time point	Data to be included (i.e. from participants first dose up to date/study day specified)
On- and post-	1-52	- Up to EOS/ EW/study conclusion date*/date of death

Asthma Exacerbations		
treatment	1-24	
 
- If participants planned EOS visit is week 24: EOS/EW visit/study conclusion date*/date of death
 
- If participants planned EOS visit is later than week 24 use data up to the minimum of study day 169, EW, lost to follow up*, date of death.
 

	25-52	
 
- If participants planned EOS visit is later than week 24 and they have not withdrawn from the study before study day 170, then data from day 170 to EW/EOS /study conclusion date*/date of death will be included in the analysis.
 
- Data from participants who have withdrawn from study before study day 170 or whose planned EOS visit was week 24 will be excluded from these summaries.
 

On- and post-treatment sensitivity analysis	1-52	
 
- For participants with an EOS visit, all data up to the EOS visit will be included
 
- For participants without an EOS visit, all data available plus imputed data up to the participants planned EOS visit will be included.
 

On-treatment	1-52	
 
- If a participant does not withdraw from treatment prior to withdrawing from/completing the study (or being lost to follow up or dying) then up to last treatment date.
 
- If a participant withdraws from treatment prior to withdrawing/completing the study (or being lost to follow up or dying) then up to last treatment date+1
 

	1-24	
 
- If a participant's planned EOS visit is week 24 and the participant does not withdraw from treatment prior to withdrawing from/completing the study (or being lost to follow up or dying): Last date of treatment
 
- If a participant's planned EOS visit is week 24 and the participant withdraws from treatment prior to withdrawing from/completing the study (or being lost to follow up or dying)): Last date of treatment +1
 
- If a participant's planned EOS is later than week 24 and participant does not withdraw from treatment prior to withdrawing from/completing the study (or being lost to follow up or dying): use the minimum of (169, Last treatment date)
 
- If a participant's planned EOS is later than week 24 and participant withdraws from treatment prior to withdrawing from/completing the study (or being lost to follow up or dying): use the minimum of (169, Last treatment date+1)
 

	25-52	
 
- If participants planned EOS visit is later than week 24 and they have not withdrawn from the treatment before study day 170 then data from day 170 up to the following timepoint will be used:                             
 
o If the participant does not withdraw from treatment
 
 
 

Asthma Exacerbations	
	
prior to withdrawing from/completing the study (or being lost to follow up or dying): Last date of treatment
 
 
○ If the participant withdraws from treatment prior to withdrawing from/completing the study (or being lost to follow up or dying): Last date of treatment+1
 
- Data from participants who have withdrawn from treatment before study day 170 or whose planned EOS visit was week 24 will be excluded from these summaries.
 

*if no study conclusion date, then use last contact date.	

 
• Denominators will be based on the number of participants with data available for the period being summarized.
 
• Exacerbations separated by less than 7 days will be treated as a continuation of the same exacerbation
 
• The duration of an exacerbation will be calculated as exacerbation resolution date or date of death - exacerbation onset date + 1.
 
	
Time to First Exacerbation	

 
• On- and Post-Treatment Exacerbations: The time to first exacerbation will be calculated as exacerbation onset date of first exacerbation – date of start of treatment+1. Participants will be represented from their Day 1 date to the start date of their first exacerbation up to and including the end of study date/early withdrawal date day. Participants that have not experienced an exacerbation on or before the end of study date/early withdrawal/ lost to follow up study/ date of death day are censored at the end of study date/early withdrawal date /study conclusion date (or date of last contact if no study conclusion date)/ date of death.
 
	

Asthma Control Questionnaire (ACQ)
General

Scoring instructions can be found Asthma Control Questionnaire: Background, Administration and Analysis, May, 2012.
 
The ACQ consists of seven attributes of asthma control (denoted as ACQ-7), and is to be administered on all scheduled clinic visits. Six attributes (ACQ-6), to be self-completed by the participant in a 6-item questionnaire, enquire about the frequency and/or severity of symptoms over the previous week in the following sequential order on: nocturnal awakening, symptoms on waking in the morning, activity limitation, shortness of breath, wheeze, and rescue medication use. ACQ-5 consists of the first five questions of ACQ, measuring asthma symptoms. The seventh attribute measures the lung function, which will be included via study visit spirometry assessment on pre-bronchodilator FEV1 % predicted value using Quanjer equation [Quanjer 2012]. The score for ACQ-5, ACQ-6, or ACQ-7 is the mean of the 5, 6 or 7 items, respectively.
 
 
• All 7 items of ACQ have response on 0-6 ordinal scale (0=no impairment/limitation, 6=total impairment/ limitation). For each version of ACQ (5, 6, 7), the total score is calculated as the
 

